For these reasons, we seek to develop and test a social media based intervention for cannabis use among EAs, delivered by health coaches who will be similar age or slightly

Full Study Title: Harnessing social media to reduce cannabis use among adolescents and emerging adults in an urban emergency department

older peers (i.e. clinical practicum students, bachelor's level psychology students, master's level public health and social work students). The guiding framework for this intervention can be found in Figure 1.

Objective

The specific aims of this clinical trial is to:

Conduct a randomized clinical trial of the SnapCoach intervention, where we will examine feasibility and acceptability of the SnapCoach Intervention as our primary outcome measures. As exploratory, other outcomes we will examine the preliminary efficacy of SnapCoach (vs. usual care control with attention-placebo; N=approximately 50 per group) on cannabis use (quantity, frequency) and consequences.

We will conduct a randomized clinical trial (RCT), to examine the feasibility, acceptability, and initial efficacy of the SnapCoach intervention. Our goal is to recruit N = 100 participants (as our target N) meeting eligibility criteria, who will complete baseline measures, and be randomized to receive the SnapCoach intervention or a control condition. They will participate in the 4-week intervention/control condition, with a post-test administered at 1-month post-baseline (i.e., end of 4-week intervention period) and a follow-up assessment of outcomes at 3-months post-baseline.

Primary outcomes are feasibility and acceptability of the Snapcoach intervention. Other exploratory outcomes include measures of cannabis quantity and frequency and consequences measured at the 3-month follow-up, examining the effect of the intervention on other substance use (alcohol, other drugs), analyses of moderators and mediators (e.g., sex, cannabis use motives), identification of the most engaging intervention content, dose-response analyses, and measurement of intervention delivery costs.

Aim 2 Methods:

Enrollment

Target enrollment is 100 emerging adults (approximately 50% males and 50% females) between the ages of 18-25, in a 2-arm pilot RCT of SnapCoach compared to an enhanced usual care (EUC) with attention placebo for EAs with weekly cannabis use.

Recruitment Procedures

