Demographics: Age, Sex, Race, Ethnicity (adapted from national surveys, e.g., the Youth Risk Behavior Survey ³⁹)	S
Demographics: Gender identity, Sexual Orientation, School Status, Employment, Living Situation, Children, Marital Status, Pregnancy (adapted from national surveys, e.g., the Youth Risk Behavior Survey ³⁹)	B,3M
Demographic: Parents and Personal Income ^{86,87}	B
Service Utilization: ER and Urgent Care ^{86,87}	B,3M
1-minute delay discounting task ⁸⁴	S,1M,3M
Snapchat involvement (modified) ^{22,40,41,42}	S
Comprehensive Marijuana Motives (modified) ⁴³	B,3M
Perceived risk of cannabis (modified for different cannabis modalities) ⁴⁴	S,1M,3M
Importance, Self-Efficacy, Intention Rulers ^{45,46}	B,I,1M,3M
Cannabis acquisition, strain, and medical marijuana ^{47,48,49,50,51,74}	
Cannabis acquisition	B,1M,3M
Preferred Marijuana Strain	B
Medical Marijuana	S,3M
NIDA modified ASSIST ^{65,66,85}	S,3M
Alcohol use frequency (AUDIT-C) ⁷³	S,3M
Tobacco and Nicotine use (modified) ⁶⁵	S,1M,3M
Mental health: Patient Health Questionnaire-2; Generalized Anxiety Disorder-2 ^{52,53,54,55,56,57,58,59,60,61}	B,1M,3M
Protective Behavioral Strategies for Marijuana (modified) ⁷⁷	B,3M
Gun Carriage ^{75,76}	B
Hope ⁷⁸	B,1M,3M

Peer/Social Influences
	
Cannabis online norms and exposure ^{64,41}	B,1M,3M

Exploratory Outcomes
	

Full Study Title: Harnessing social media to reduce cannabis use among adolescents and emerging adults in an urban emergency department

Cannabis use method, frequency and quantity ⁷⁴ (modified) Smoke, Vape, and Dab (frequency, quantity) Drink and all methods combined (frequency, quantity) Number of days all methods combined Number of days vaped	S,3M B,3M B,1M,3M 1M
Cannabis and Other Drug Use Frequency, Alcohol Quantity/Frequency(TLFB) ^{67,68,69,70}	B,3M
Brief Marijuana Adolescent Consequences Questionnaire (modified) ⁷¹	B,3M
Impaired driving (modified) ⁷²	B,3M
Primary Outcomes: Feasibility/Acceptability of Intervention	
Brief Intervention acceptability ratings (created for this study)	I
Snapchat acceptability ratings (created for this study)	1M
Brief intervention feasibility (e.g., % of participants completing brief intervention)	I
Snapchat health coaching feasibility (e.g., % of participants who complete process of adding health coach on Snapchat, % of participants who reply to at least 1 Snapchat message)	I,1M

Data Management and Analysis

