Randomized participants will be included in intent-to-treat analyses, regardless of group engagement. By design, groups will be balanced based on sex, age, and more than once a day cannabis use, using urn randomization in blocks of 4; we will validate randomization by evaluating covariate balance between groups. If significant differences that could be confounding emerge, we will adjust for those variables or conduct stratified analyses.

Analyses pertaining to primary outcomes of feasibility and acceptability of the intervention are primarily descriptive in nature (e.g., % completing the assigned intervention condition, % engaging in Snapchat messaging, ratings of intervention satisfaction).

For analyses of other exploratory outcomes pertaining to cannabis use, alcohol, and drug use, we will first compare groups on cannabis quantity and frequency using basic two sample comparisons, operating on the pre-post differences (e.g., 3M-Baseline) to test for treatment effects. Our first choice will be a two-sample *t*-test to compare the pre-post differences between groups; considering non-parametric alternatives as needed. To assess changes in the dependent measures (e.g., use days, quantity, cannabis consequences) over follow-up we will use generalized linear mixed models (GLMMs) to jointly study the 1M and 3M outcomes, where possible, while adjusting for correlations between data points (e.g. repeated measurements on individuals). While adjustment for the baseline measurement is important for guarding against regression to the mean in RCTs¹⁹⁵, using this baseline adjustment at every time point can result

Full Study Title: Harnessing social media to reduce cannabis use among adolescents and emerging adults in an urban emergency department

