in overestimation of the treatment effect when there are multiple follow-up points. It has been shown that baseline adjustment at only the first follow-up (1M in this case) corrects this overestimation while also guarding against regression to the mean, which will be our approach. Within this framework, we will conduct exploratory sub-analyses of whether the intervention effect is accumulating or weakening over time, by including time-by-group interactions. If the need is ascertained, we will control for confounders through their inclusion in the model as covariates. Our initial specification will be a linear mixed effects model (with Gaussian error distribution) with only a random intercept to capture within-individual dependence, but this choice will be scrutinized by examining model diagnostics and evaluating the veracity of modeling assumptions. As the need is ascertained, we will examine other distributional choices (e.g., Poisson, Negative Binomial) and more complex random effects structures (e.g., autoregressive).

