Aim 2: The sample size is $N = 100$ (approximately 50 per group). For our primary analytic goal – examining feasibility and acceptability this is acceptable. With regard to other exploratory analyses estimating treatment effects – we are comparing two groups of size $n = 50$. Assuming no substantial covariate adjustment is needed, testing the significance of the treatment effect at a single time point will be equivalent to the comparison of two means, for which we use Cohen's D (0.2: small, 0.5: medium, 0.8: large) as an effect size. Under the expected sample size, we will have sufficient power ($>80\%$) to detect effects on both our cannabis and other substance use outcomes if $d > 0.56$, a medium effect size. Although the required effect size is non-negligible, the proposed pilot will provide the critical data necessary to inform the power analyses for a subsequent efficacy trial. While effect sizes from pilot studies

Full Study Title: Harnessing social media to reduce cannabis use among adolescents and emerging adults in an urban emergency department

can have large standard errors and be unstable,²⁰² we can use these pilot data to estimate point estimates and confidence intervals for our treatment effect sizes using the R package MBESS²⁰³.

Data Confidentiality Plans

Our study team will take the following steps to minimize potential confidentiality breaches. As done in prior research and deemed HIPAA compliant by the IRBs at University of Michigan (UM) and HMC by use of a waiver of HIPAA authorization, minimal clinical data will be collected on ED patients who refuse to participate in the screening survey, and on ED patients who the research assistants fail to approach or contact (for remote recruitment). ED-based intervention, TLFB assessment sessions and any phone interviews (e.g., in the event a person cannot attend a follow-up in person, or during remote recruitment, we can administer the TLFB by phone) will be audio-recorded and will be destroyed after the conclusion of the study.

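### The simple group comparison is a complete-case change-score test, and for most cannabis outcomes the plan has no rule for a missing 3-month value

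*Combined protocol and SAP*

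**What the plan says.** All the analysis text is in the Data Management and Analysis section of the combined protocol and SAP.

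- **Analysis population:** "Randomized participants will be included in intent-to-treat analyses, regardless of group engagement".
- **Simple comparison:** cannabis quantity and frequency are first compared between arms "operating on the pre-post differences (e.g., 3M-Baseline) to test for treatment effects". The section continues: "Our first choice will be a two-sample *t*-test to compare the pre-post differences between groups". Non-parametric tests are the stated fallback.
- **Longitudinal model:** the next step is "generalized linear mixed models (GLMMs) to jointly study the 1M and 3M outcomes, where possible". The starting form is given: "Our initial specification will be a linear mixed effects model (with Gaussian error distribution) with only a random intercept". Baseline adjustment is to be made at the 1-month follow-up only.
- **When outcomes are collected (Table 1):** the cannabis method, frequency and quantity row ends with "Number of days all methods combined Number of days vaped". The row was flattened in extraction. Matching items to codes in order, days of use by all methods combined is collected at baseline, 1 month and 3 months, and days vaped at 1 month only. The quantity items have a screening or baseline value and a 3-month value. Timeline Follow-Back frequency and consequences are collected at baseline and 3 months.
- **Status:** the Objective section states "Primary outcomes are feasibility and acceptability of the Snapcoach intervention". Cannabis use and consequences are exploratory.

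The documents give no missing-data method, no expected follow-up rate, and no definition of the set analysed when the 3-month value is absent.

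**The concern.** A change score needs both values. A participant randomised and then lost before 3 months cannot enter a t-test of 3 months minus baseline, whatever the analysis population is called. The same test makes no use of a 1-month value.

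For use days the mixed model fills this gap, because a likelihood fit keeps a participant who has 1 month but not 3 months. The other cannabis outcomes have only one follow-up. A joint model of 1 and 3 months is then not available, and baseline adjustment at 1 month has no 1-month value to act on. For these outcomes the complete-case change score carries the efficacy result.

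Two things are at stake. One is bias, if loss differs between arms and is related to change in use. The other is precision, because complete cases are fewer and an unadjusted change score is a less efficient contrast than a baseline-adjusted one. The Power calculation and sample size section says that the pilot's effect sizes and intervals will inform a later efficacy trial, so both would carry forward.

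**Working it through.** **Inputs.** From the documents: about 50 per arm, detectable d = 0.56, power above 80%. Assumed, because not stated: two-sided alpha 0.05, loss at 3 months of 10% to 30% (equal in both arms for the power figures), equal variances over time, and the correlations given below.

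**1. The plan's own figure.** Detectable d = (1.960 + 0.842) × √(2/50) = 0.560. Power at d = 0.56 is 79.96% (normal approximation) or 79.2% (noncentral t). The stated figure reproduces, with all 50 per arm analysed.

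**2. The same test on complete cases.** Put n = 50 × (1 − loss) into the same formula:

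| Assumed loss | n per arm | Power at d = 0.56, normal (t) | Detectable d, normal (t) |
|---|---|---|---|
| 10% | 45 | 75.7% (74.8%) | 0.591 (0.597) |
| 20% | 40 | 70.7% (69.6%) | 0.627 (0.634) |
| 30% | 35 | 64.9% (63.7%) | 0.670 (0.679) |

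**3. What the 1-month use days add.** Assume equal correlation between all three time points and 1 month fully observed. The changes (1 month − baseline) and (3 months − baseline) each have variance 2(1 − ρ) and covariance 1 − ρ, so they correlate 0.5 whatever ρ is. The variance of the 3-month contrast is then multiplied by 1 − 0.25 × loss:

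- 10% loss: 0.975, equivalent to 45/0.975 = 46.2 per arm
- 20% loss: 0.950, equivalent to 40/0.950 = 42.1 per arm, with power about 73%
- 30% loss: 0.925, equivalent to 35/0.925 = 37.8 per arm

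The recovery is about 1 to 3 participants per arm. Once baseline is adjusted for, 0.25 is replaced by [ρ/(1 + ρ)]², which is 0.05 at ρ = 0.3 and 0.17 at ρ = 0.7, so the gain is smaller still.

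**4. What baseline adjustment adds.** The change score has variance 2(1 − ρ)σ². Regression on baseline has residual variance (1 − ρ²)σ² in large samples. The ratio is (1 + ρ)/2:

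- ρ = 0.3: 0.65, variance 35% lower
- ρ = 0.5: 0.75, variance 25% lower
- ρ = 0.7: 0.85, variance 15% lower

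This exceeds the gain in step 3, and it applies to outcomes that have no 1-month value.

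**5. Possible bias.** In each arm, the mean for everyone equals the retained mean plus (proportion lost) × (lost mean − retained mean). If that gap is the same in both arms, the bias is (difference in loss) × gap. With assumed values, 0.10 × 0.5 SD = 0.05 SD and 0.15 × 1 SD = 0.15 SD. The second is 0.15/0.56 = 27% of the detectable effect.

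Bias is not automatic. A simulation of 4,000 trials used no true effect, correlation 0.6, and loss in one arm depending on the 1-month level (mean retention 83% and 81%). The mean error was −0.002 SD for the change-score test and −0.001 SD for a likelihood estimate. With equal correlations, the 1-month level is unrelated to change at 3 months, so the gap in the formula is zero. Bias needs loss that is related to the change itself.

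**The case against.** The strongest reply is that the plan already contains most of the remedy. The mixed model comes directly after the t-test, uses the 1-month data, and is close to what a reviewer would ask for. The t-test is a first choice only against non-parametric tests within the simple comparison. Nothing ranks it above the mixed model, and 3 months minus baseline is given as an example. All of this stands for use days, where what remains is to say which analysis leads. It does not help quantity, Timeline Follow-Back frequency or consequences. For these, 3 months is the only follow-up, so the example is the only change score available.

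A reader might infer that the plan contradicts its intent-to-treat statement. It does not. The sentence concerns people who do not engage and does not promise an outcome value for everyone. A t-test that keeps non-engagers with 3-month data is consistent with it. What is missing is a rule for absent values.

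A reader might also infer that 1-month data are thrown away. That is true of the t-test but not of the plan as a whole.

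Differential loss may be doubted too. Both arms watch coach videos, add coaches and receive snaps. Payments, modes of assessment and reminders are described without distinction by arm. On the other side, only intervention participants get motivational discussion in reply, and Snapchat is one of the reminder channels. Unequal loss is therefore possible, but nothing in the documents shows it.

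**Conclusion.** The point holds in a limited form. The simple comparison is a complete-case analysis. For the cannabis outcomes without a 1-month value it is in effect the efficacy analysis, with no missing-data rule behind it. This rests on reading the flattened Table 1 row in order.

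The loss of power is moderate: from about 80% to about 65% to 76% at d = 0.56, for an assumed 30% to 10% loss. Only a small part of that can be recovered from 1-month data. The stronger reasons to change are the gain from baseline adjustment (15% to 35% of variance at assumed correlations of 0.7 to 0.3) and a defined analysis set. Bias of 0.05 to 0.15 SD is an illustration under assumed imbalance, not an estimate for this trial.

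Efficacy is exploratory and the primary outcomes are descriptive, so severity is modest. The change is still worth making, because it replaces a stated method with a better one using data already collected.

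**What to change.** In Data Management and Analysis:

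1. **Use days.** Name the planned likelihood mixed model as the lead analysis. Fit it to all randomised participants with any follow-up, adjust it for baseline, and report the 3-month contrast between arms.
2. **Outcomes without a 1-month value.** Replace the change-score t-test with regression of the 3-month value on arm, the baseline (or screening) value and the balancing factors: sex, age group and use more than once a day. Keep the plan's option of count distributions where the data call for them.
3. **Missing 3-month values for those outcomes.** Use multiple imputation within arm, from the covariates of the analysis model plus 1-month use days. State that this assumes missing at random, and add a sensitivity analysis that departs from it.
4. **The t-test.** Keep it as a supportive result, labelled complete-case, with the number analysed in each arm.
5. **Power.** In the Power calculation and sample size section, give the detectable effect at the expected 3-month follow-up rate as well as at 50 per arm.

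The cost is SAP wording and a little more analysis work. No new data are needed. The price is reliance on a missing-at-random assumption, which is why the sensitivity analysis is part of the change.

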Participants will be recruited either during or post-emergency department (ED; including urgent care) visit at Hurley Medical Center (HMC) which is a public, academic, Level-1 Trauma Center located in Flint, Michigan. Enrollment will focus on recruiting approximately 50% males and 50% females. Potential participants will be screened for eligibility using a 5-10 minute screening survey. Randomization to conditions will be balanced based on sex (male, female), age (ages 18-20, ages 21-25), and more than once a day cannabis use, using urn randomization in blocks of 4.

Modifications to recruitment procedures for the purposes of remote recruitment are described here:

For remote recruitment, RAs will contact ED patients ages 18-25 who meet screening inclusion criteria (listed below in "Study Eligibility Criteria") within 60 days of discharge to invite them to consent and complete a web-based screening survey. RAs

Full Study Title: Harnessing social media to reduce cannabis use among adolescents and emerging adults in an urban emergency department

will determine who to contact by viewing HMC's ED medical records (same records viewed as during in-person recruitment), they may send a text message to let the participant know we will be contacting them. Using contact information obtained from the medical record, RAs will follow a phone recruitment script for these procedures, obtain verbal informed consent prior to starting the screening survey and document RA name and date consent is obtained.

After consenting, interested participants may choose to self-administer the survey online or complete an RA-administered version over the phone. For verbally consented participants completing the survey online, a copy of the screening consent form will appear at the beginning of the survey. Other participants may prefer to interact with us via text message, in this case we may adapt the phone script for text messaging, and we will obtain electronic consent at the beginning of the screening survey. Participants recruited remotely will not receive a token gift for completing the screening survey.

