Other analyses. *Moderation:* To assess potential moderators we will include interactions with treatment group in the GLMM models above. Potential effect modifiers will include sex and age. *Mediation:* To test if cannabis motives and other variables (e.g., mental health symptoms) mediate treatment effects, we will use Imai's causal mediation analysis framework, that is robustly implemented in the R package *mediation*. Traditional mediation analysis can be susceptible to bias; one source of this bias is the limitation to the classes of statistical models (e.g. the linear structural model of Baron and Kenny), that can be accommodated in traditional mediation analysis. Under technical assumptions of sequential ignorability, mediation effects are identifiable using Imai's framework when models for the mediator and for the outcome that are non-linear, have discrete (nominal or ordinal) or continuous outcomes, include random effects, or are non-parametric. *Engagement:* Daily content ratings assessed by tallies from Snapchat messages logs (e.g., content, messages sent/received) will be calculated for different content areas (e.g., free time, stress, drug/alcohol-related) and assessed descriptively to see types of content with high response rates. *Cost:* To estimate intervention we will calculate summary statistics for the total intervention-specific costs and mean costs per participant, with confidence intervals. Costs will be reported with/without start-up and development, for example, including costs for recruiting and training coaches as well as their clinical supervision. As with prior work, net costs (savings) will be calculated by subtracting mean costs per participant in the control group from costs per participant for the assigned condition, also calculating the incremental cost effectiveness ratio (difference in mean cost of intervention vs. control divided by difference in mean effectiveness between intervention and control). Change in health benefits will be measured as the difference in cannabis consequences per month for the intervention vs. the control, expressed in dollars per consequence averted. Sensitivity analyses to evaluate alternate assumptions for estimated costs will be conducted. Given likely skewness, we will identify appropriate methods for generating confidence intervals that do not rely on the normal distribution (e.g., non-parametric bootstrapping).

Power calculation and sample size

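### The three factors balanced at randomisation are not committed to the treatment-effect models, and other adjustment hangs on an undefined baseline significance check

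*Combined protocol and SAP*

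**What the plan says.** The section Recruitment Procedures states: "Randomization to conditions will be balanced based on sex (male, female), age (ages 18-20, ages 21-25), and more than once a day cannabis use". The allocation method is described as an urn scheme in blocks of four. Data Management and Analysis repeats the commitment: "By design, groups will be balanced based on sex, age, and more than once a day cannabis use".

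The same section then describes the analyses of cannabis, alcohol and other drug use:

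- **First comparison.** The groups are compared "using basic two sample comparisons, operating on the pre-post differences (e.g., 3M-Baseline) to test for treatment effects". The preferred test is a two-sample t-test, with a non-parametric test as fallback. No covariates are named.
- **Mixed model.** The one adjustment planned outright is for the baseline value of the outcome, at the 1-month visit. Beyond that: "If the need is ascertained, we will control for confounders through their inclusion in the model as covariates".
- **General covariate rule.** "If significant differences that could be confounding emerge, we will adjust for those variables or conduct stratified analyses".
- **Moderation.** "Potential effect modifiers will include sex and age". These are interaction models. More-than-once-daily use is not named in any model.

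Power calculation and sample size gives more than 80% power for d above 0.56 with 50 per group, on the stated premise that no substantial covariate adjustment is needed. On the use of the results it says: "we can use these pilot data to estimate point estimates and confidence intervals for our treatment effect sizes". The stated aim there is to inform the power analysis of a later efficacy trial.

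**The concern.** When allocation is balanced on a factor that predicts the outcome, the treatment estimate no longer varies through chance imbalance in that factor. An analysis that omits the factor still counts its variance as noise. The standard error is then too large, the interval too wide, and the test rejects too seldom under the null.

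The covariate rule cannot repair this. It reacts to significant imbalance, which balanced allocation is designed to prevent. For all other variables it starts from a chance difference between groups rather than from how strongly the variable predicts the outcome. It names no test, threshold or candidate list, and leaves open whether to adjust or stratify. The covariate set would therefore be settled after the data are seen.

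The primary feasibility and acceptability results are descriptive and not affected. What is at stake is the precision of the exploratory effect estimates, which are one of the pilot's stated products.

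**Working it through.** **1. The plan's own figure.** Inputs: 50 per arm and d = 0.56 (Power calculation and sample size). Alpha is not stated; two-sided 0.05 is assumed. Normal approximation: SE = √(2/50) = 0.2 SD, power 79.96%, detectable d at 80% power (1.960 + 0.842) × 0.2 = 0.560. With the t distribution: power 79.2%, detectable d 0.566. The stated figure is reproduced. One-sided 0.05 would give 87.6%, so two-sided 0.05 is the implied setting.

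**2. Effect of adjustment, normal approximation.** The documents give no R² for the three factors, so 10%, 20% and 30% of the variance of the analysed outcome are assumed. Under near-exact balance the estimate's true SE is s = 0.2 × √(1 − R²), while the unadjusted test uses 0.2.

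| Quantity | Formula | R² 10% | 20% | 30% |
|---|---|---|---|---|
| Unadjusted type I error | 2 × (1 − Φ(1.96/√(1 − R²))) | 3.9% | 2.8% | 1.9% |
| Unadjusted power at d = 0.56 | Φ((0.56 − 0.392)/s) | 81.2% | 82.6% | 84.2% |
| Adjusted power at d = 0.56 | Φ(0.56/s − 1.96) | 83.9% | 87.9% | 91.7% |
| Adjusted CI half-width, SD | t(0.975, 95) × s | 0.377 | 0.355 | 0.332 |
| Equivalent n per arm | 50/(1 − R²) | 55.6 | 62.5 | 71.4 |

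The unadjusted half-width is t(0.975, 98) × 0.2 = 0.397 SD. At R² = 0 the only cost is three degrees of freedom: power goes from 79.17% to 79.15%.

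**3. Simulation.** The allocation wording admits more than one scheme, so three were simulated: N = 100, three independent 50% factors with equal effects, 8,000 runs, least squares with and without the factors. Monte Carlo error is about 0.2 points for type I error.

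| Scheme | Unadjusted type I error at R² 10/20/30% | Any balancing factor significant at 5% |
|---|---|---|
| Stratified permuted blocks of 4 | 3.9 / 3.3 / 2.1% | 0.0% |
| Urn within each stratum | 4.1 / 3.6 / 3.5% | 0.6% |
| Multi-factor urn | 4.5 / 3.7 / 2.9% | 0.9% |

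Repeat runs put the 3.5% entry at 3.0% to 3.2%, which changes nothing below. Adjusted type I error was 4.6% to 5.4% throughout. With the multi-factor urn, power at d = 0.56 rose from 79% to 82%, 81% to 87% and 81% to 91%. With an assumed 15% dropout it rose from 73% to 76%, 80% and 85%. Interval width fell by about 5%, 10% and 16%.

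**4. Is 10% to 20% plausible?** For cannabis frequency, the use factor is a category of baseline use, and a change score subtracts baseline. Assume bivariate normality, equal variances, baseline-to-3-month correlation ρ and a proportion p in one category. The factor alone then explains R² = ((1 − ρ)/2) × φ(z_p)²/(p(1 − p)) of the change-score variance:

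- ρ = 0.7, p = 0.2: 0.073
- ρ = 0.5, p = 0.5: 0.159
- ρ = 0.3, p = 0.5: 0.223

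For alcohol or other-drug outcomes R² may be near zero.

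**5. The trigger for other variables.** If k independent baseline variables were each tested at 5%, the chance of at least one flag under sound randomisation is 1 − 0.95^k: 40% for k = 10, 54% for 15, 64% for 20. Both k and the 5% level are assumptions, because the plan gives neither.

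**The case against.** The strongest reply is that this is a matter of efficiency in exploratory analyses of a pilot. The unadjusted analysis is valid and slightly conservative, the power statement discloses its premise, and the primary outcomes are untouched. All of that stands, and it limits the weight of the point.

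The size rests on an assumed R². That also stands. The argument in step 4 supports roughly 10% to 20%, for cannabis frequency only. It treats the use factor as a cut of the analysed variable, which is imperfect for a bounded count of use days. The 30% column is an upper illustration.

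The gain from the use factor is largely regression to the mean. In the model of step 4, continuous baseline alone explains (1 − ρ)/2, that is 15% to 35%, and the use factor adds nothing once baseline is included. So the computed gain belongs to the change-score comparison; none has been computed for the mixed model. But the mixed model's baseline adjustment is tied to 1 month. Table 1 lists the timeline follow-back measures, the consequences questionnaire and all-methods quantity at baseline and 3 months only. For these the change-score comparison carries most of the weight, and sex and age are not absorbed by baseline use.

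The trigger is not purely a significance rule, since it also asks whether a difference could confound. That is true, but no criterion for this is given.

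Finally, dividing an adjusted effect by the residual SD would raise d by 1/√(1 − R²) − 1, that is 5%, 12% or 20%. This is a fair caution, and stating the standardiser meets it.

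**Conclusion.** The concern holds. The plan balances allocation on three factors, commits none of them to a main treatment-effect analysis, and relies on a trigger those factors will almost never meet. Omitting them makes intervals wider than the design earned: about 5% to 10% of interval width at an assumed R² of 10% to 20%, or roughly 3 to 6 power points at d = 0.56. It does not inflate false positives. The open choice of other covariates is a separate weakness whose effect on the estimates has not been quantified.

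The stated d = 0.56 is sound. The gain depends on an R² the documents do not supply and may be nil for some outcomes, but then the cost is also negligible. The change is worth making because the intervals are meant to feed the design of a later trial; the pilot's primary conclusions do not depend on it.

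**What to change.** In Data Management and Analysis:

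- Replace the significance trigger with a fixed rule: every treatment-effect model includes sex, age group (18-20, 21-25) and more-than-once-daily cannabis use.
- Run the change-score comparison as a linear model with treatment and these three covariates. Keep the two-sample t-test or its non-parametric alternative as a sensitivity analysis.
- Add the same three covariates to the mixed model, including any Poisson or negative binomial version, and leave its baseline-outcome handling as planned.
- Report baseline balance descriptively, and label adjustment for any other variable as a sensitivity analysis.
- Where an adjusted effect is reported as Cohen's d, say that it is standardised by the unadjusted SD.

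The cost is two revised sentences, one added clause and the note on the standardiser. All three variables must be known before randomisation, so nothing new is collected. The adjustment uses three of about 98 degrees of freedom.
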